During any routine clinic meeting, patients scoring highly on the SNOT-22 questionnaire will be asked whether they wish to take part in the study. The healthcare professionals will ensure the patient has read the information leaflet, answering any questions they may have with regards to the study. Patients who wish to proceed will be asked to give informed consent and will become a participant of the study. Participants will be randomly assigned into two groups; Group one will follow the standard NHS nasal rinse protocol, and group two will follow a modified NHS nasal rinse protocol which requires the addition of manuka honey (supplied to the participants). Participants will then follow the nasal rinse procedure (with/without manuka honey) daily for 30 days.

As part of routine clinical care, patients return to the AWACF centre approximately one month after routine clinic meeting. During this meeting the same tests are completed and their results from the previous meeting are explained to them. A treatment plan is then agreed with the patient. Participants of the study will supply a nasal swab, sinus rinse sample, and sputum sample (all part of standard care) along with copies of their SNOT-22 and CFQ-UK questionnaires. Any effects manuka honey has on the questionnaire scores, the amount/diversity of bacteria within the sino-nasal area, and/or the structural composition of the sputum will be analysed and determined.

Conventional microbial culture analysis will be completed along with microbiota analysis using DNA extracted from bacteria within sputum, sinus rinse, and swab. This high resolution, cultivation independent method analyses all the bacteria present in the samples including those that are deemed "unculturable". Understanding the total microbiota and the effect of honey on these organisms will provide an all-encompassing picture of the therapeutic benefit the proposed sinus rinse protocol. Fourier transform infrared spectroscopy will be used to determine if the manuka honey rinse protocol causes any molecular structural changes to sputum mucus (secreted mucin glycoprotein) composition as mucin glycan composition maybe an indicator of disease state in cystic fibrosis (Schulz et al., 2007).

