4.2 Secondary Objectives

Objective	Outcome Measure / Endpoint
Does the addition of manuka honey to a sinus rinse alter the quality of life of patients with cystic fibrosis?	Quality of life questionnaires (CFQ-R) will be completed before and after the use of a sinus rinse with/without manuka honey.
Does the addition of manuka honey to a sinus rinse impact on the bacterial type/amount found in the nasal/paranasal cavities of patients with cystic fibrosis?	Swabs, a sinus rinse wash sample and a sputum sample for each participant will be collected before and after the use of a sinus rinse with/without manuka honey. Bacteria amount and types will be analysed in each sample.
Does the addition of manuka honey to a sinus rinse protocol change the structure of sputum mucus in patients with cystic fibrosis?	Sputum samples from each participant will be analysed before and after the use of a sinus rinse with/without manuka honey by fourier transform infrared spectroscopy.

Bwrdd lechyd Prifysgol Caerdydd a'r Fro Cardiff and Vale University Health Board

5. Study Design

This is a single site study to be run at the AWACFC based in University Hospital Llandough (Cardiff and Vale Health Board) when patients attend any routine clinic meeting. The work on site will be carried out by the clinical research team as per the delegation of duties log.

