Participants will then be given a nasal rinse kit (with/without manuka honey depending on the group they have been assigned), a set of instructions on how to use the kit, and a compliance diary. Participants will use their respective kits as per the instructions daily and fill in the compliance diary, ensuring to make note of any observations in the compliance diary. Participants will then return to the AWACFC 31 days (+7/- 20 days) later for their standard follow up appointment (Visit 2). During this visit a second set of data/samples will be collected as per below:

- SNOT-22 questionnaire.
- Cystic Fibrosis Quality of life (CFQ-R) questionnaire.
- Clinical Record Form (CRF) data.
- Nasal swab.
- Sputum sample.
- Nasal rinse wash solution.

Following the collection of samples by the clinical research team during visit 1 and 2, they will be collected by the academic research team whom will process the nasal swab, sputum sample, and nasal rinse wash solution the same day, extracting bacteria and bacterial DNA from the samples. The structural composition of the sputum mucus will also be determined from the sputum sample. Other analysis of the samples we be completed at a later date where the amount/types of bacteria present will be determined.

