12.1 Description of Statistical Methods

Qualitative analysis will include the difference between the SNOT-22 and quality of life questionnaire (CFQ-R) scores being assessed before and after treatment within and between both patient groups (with/without manuka honey). To determine if manuka honey caused a change in the amount/type(s) of bacteria present compared to the control group, a contingency table with odds ratio will be prepared taking into account co variants. Infrared spectra will be baseline corrected and vector normalised. Absorbance from specific infrared wavenumbers representative of mucin glycan molecular structures will be compared against in-house sputum spectral libraries to determine increase or decrease in glycosylation patterns as well as structural changes post-treatment. Comparisons in absorbance at key wavenumbers between groups will be analysed using ANOVA.

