12.3 Analysis of Outcome Measures/Endpoints

All participant data will be analysed by the academic research team after the end point of the study. The data will be sorted into the two treatment groups before analysis is carried out. The

primary outcome measures will be to determine whether the SNOT-22 score of the manuka honey treatment group has improved compared to the standard treatment. The secondary outcomes will be to see if; the lifestyle questionnaire scores have improved, the amount/type(s) of bacteria has changed, and whether the structure/composition of sputum mucus has changed in the same two groups. If any participants withdrew before the second visit/second set of samples were taken then that data will be excluded from analysis.

Bwrdd lechyd Prifysgol Caerdydd a'r Fro Cardiff and Vale University Health Board

13. Data Management

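### Section 12.1 does not say how a participant's Visit 1 sputum spectrum enters the infrared analysis; ANCOVA on the Visit 1 value would use data already collected and add precision

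*Combined protocol and SAP*

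**What the plan says.** The infrared analysis is set out in section 12.1 of the protocol in three steps.

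- Pre-processing: "Infrared spectra will be baseline corrected and vector normalised". The baseline here is that of the spectrum, not the Visit 1 measurement.
- Direction of change: absorbance at mucin glycan wavenumbers is "compared against in-house sputum spectral libraries to determine increase or decrease in glycosylation patterns as well as structural changes post-treatment".
- Test: "Comparisons in absorbance at key wavenumbers between groups will be analysed using ANOVA".

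The endpoint these steps serve is a before/after one. Section 4.2 states: "Sputum samples from each participant will be analysed before and after the use of a sinus rinse". Sections 9.1 and 9.6 list a sputum sample at Visit 1 and again at Visit 2 ("During this visit a second set of data/samples will be collected as per below"). Section 12.3 words the outcome as "whether the structure/composition of sputum mucus has changed in the same two groups".

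Section 12.1 treats the other outcomes differently. The questionnaires are described as "scores being assessed before and after treatment within and between both patient groups", and the bacterial analysis is to take covariates into account. The spectra get neither statement. The synopsis adds only the pre-processing.

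**The concern.** No step in section 12.1 names the participant's Visit 1 spectrum, whether as a covariate, in a change value, or through a participant or repeated-measures term. The ANOVA sentence does not say which visit's absorbance is analysed. The groups are most naturally the two arms, but the sentence does not rule out arm-by-visit cells.

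This matters because stable differences between patients are to be expected. Section 3 says that "mucin glycan composition maybe an indicator of disease state in cystic fibrosis", so participants may well differ in glycan absorbance before any rinse is used. An analysis that ignores Visit 1 leaves that spread in its error term, and in a trial of about 30 people the loss can be noticeable. The choice is also left open until late: under section 9.4 the academic team, which does the analysis, receives the allocations once analysis begins.

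**Working it through.** **The plan's own figure.** The protocol gives no SD, correlation, effect size or sample size for the infrared endpoint. Its minimum of 21 in section 12.2 is for SNOT-22. It reproduces as ((1.960 + 0.842) × 14.5 / 8.9)² = 20.83, rounded up to 21, but says nothing about the spectra.

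**Inputs.** The target of 30 is from section 12.2. The following are assumptions: 1:1 allocation (the ratio is not stated), so 15 per arm with usable sputum from all; two-sided alpha 0.05; equal SD at both visits; visit-to-visit correlation r from 0.3 to 0.8. Differences are in units of the between-patient SD at one visit.

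**Chance imbalance at Visit 1.** Standard error of the arm difference = √(2/15) = 0.365 SD. Probability that it exceeds 0.5 SD in either direction = 2 × (1 − Φ(0.5/0.365)) = 0.17.

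**Precision of the arm comparison.** Variance relative to a Visit 2-only comparison is 1 for Visit 2 only, 2(1 − r) for an unadjusted change score and 1 − r² for ANCOVA on Visit 1. With relative variance v, the smallest difference detectable at 80% power (normal approximation) is (1.960 + 0.842) × √(2v/15).

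| r | Visit 2 only: v, detectable | Change score: v, detectable | ANCOVA: v, detectable | Power for 1 SD: Visit 2 only / ANCOVA |
|---|---|---|---|---|
| 0.3 | 1.00, 1.02 SD | 1.40, 1.21 SD | 0.91, 0.98 SD | 78% / 82% |
| 0.5 | 1.00, 1.02 SD | 1.00, 1.02 SD | 0.75, 0.89 SD | 78% / 88% |
| 0.7 | 1.00, 1.02 SD | 0.60, 0.79 SD | 0.51, 0.73 SD | 78% / 97% |
| 0.8 | 1.00, 1.02 SD | 0.40, 0.65 SD | 0.36, 0.61 SD | 78% / 99.5% |

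The change score beats Visit 2 alone only when 2(1 − r) < 1, that is r > 0.5.

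**Small-sample caveat.** Estimating the covariate slope inflates the ANCOVA variance by about 1 + 1/(2 × 15 − 4) = 27/26 = 1.04. At r = 0.3 the ratio becomes 0.91 × 1.04 = 0.95. ANCOVA breaks even where 1 − r² = 26/27, that is r = √(1/27) = 0.19. The gain at low correlation is therefore slight.

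**Validity.** In 20,000 simulated trials at each of r = 0.3, 0.5, 0.7 and 0.9, with no true effect, a t-test on Visit 2 alone rejected in 4.8% to 5.1%.

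**Arm-by-visit cells treated as independent.** The difference in change then has an assumed variance proportional to 4/15 but a true one proportional to 4(1 − r)/15, so the test is conservative. Simulated type I error was 2.0%, 0.7%, 0.1% and about 0% at r = 0.3, 0.5, 0.7 and 0.9. Power for 1 SD was about 46–47%, against about 75% for Visit 2 alone in the same simulation.

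**The case against.** The strongest reply is that the protocol is silent about Visit 1 and does not exclude it. Sputum is collected and analysed at both visits, section 12.3 speaks of change, and it drops participants who leave before the second samples, which suits a paired analysis. Words such as increase, decrease and post-treatment also imply a pre-treatment comparator. This stands. A reader might infer from section 12.1 that the library replaces the participant's own Visit 1 spectrum as the reference, but the text does not say so. If both visits are read against the same library value L, then (V2 − L) − (V1 − L) = V2 − V1 and the library cancels. That differencing, however, is not written down either.

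A reader might also infer that the comparison targets the wrong quantity, or that an arm that is sicker at Visit 1 would bias it towards a honey effect. The documents do not support this. Allocation is randomised, so the expected arm difference at Visit 2 equals the expected arm difference in change, and chance imbalance is already reflected in the standard error of an unadjusted test. The simulated error rates agree.

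Finally, the size of the gain rests on a correlation the protocol does not give, and the endpoint is a secondary one in a study labelled feasibility/pilot. Both points are fair. They limit the weight of the finding but do not remove the gap in the text.

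**Conclusion.** The point holds as an under-specified and probably inefficient analysis. Section 12.1 plans a between-group ANOVA of absorbance and a library reading, and does not write the Visit 1 spectrum into either, although the endpoint is before/after.

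If Visit 2 is analysed alone, inference is valid but less precise than it could be: ANCOVA on Visit 1 would leave between 91% (r = 0.3) and 36% (r = 0.8) of the residual variance, before the roughly 4% small-sample inflation. If arm-by-visit cells are treated as independent, the test is conservative and loses power. Neither reading produces excess false positives.

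These sizes depend on the assumed correlation, 1:1 allocation and 15 per arm with sputum at both visits. The issue is worth correcting, but it does not threaten the trial's validity.

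**What to change.** In section 12.1:

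1. State that the in-house library is used to assign wavenumbers to glycan structures.
2. Replace the unadjusted ANOVA with ANCOVA: Visit 2 absorbance at each key wavenumber as outcome, arm as factor, and the same participant's Visit 1 absorbance at that wavenumber as covariate. Report the adjusted arm difference with its confidence interval.
3. Report Visit 2 minus Visit 1 by arm descriptively only, since an unadjusted change score is less precise than Visit 2 alone when the correlation is below 0.5.

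The cost is a wording change, to be made before allocations are released to the academic team. Both samples are already planned. Participants without a usable sputum spectrum at both visits cannot contribute to this analysis, so their number should be reported by arm.

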12.2 Number of Participants

The proposed sample size combines a power calculation and a consideration of logistical constraints. We expect to see 290 patients per year of which 50% should complete a SNOT-22 form. Of the 145 forms received around 72 (50%) should be above average. If we allow for a low recruitment rate (of 30-40%) we believe it is realistic to enrol at least 20-30 patients per year. Over the 18 months of the project we feel, therefore, a sample size of 30-40 can be realistically achieved.

Savastano (2014) published summary details of SNOT-22 scores for CF patients (who should well approximate our sample group) reporting a mean (SD) scores of 30.5(14.5). We draw our definition of a clinically significant change from Hopkins et al (2009), who propose 8.9 points. The study will be structured as a 2-sided equality trial, with before and after measurements for each participant. In order to obtain a power of 80% we would require a sample size of at least 21. We therefore propose that a target sample size of 30, since this will be both achievable and will deliver sufficient power, even allowing for drop outs.

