A clear picture that has emerged from the application of microbiome analysis to CF lung infections is that as patients age, accumulating multiple rounds of potent antibiotic therapy, the diversity of the bacteria in the lung reduces. Their infections become dominated with AMR infections such as Pseudomonas and Burkholderia. This low diversity state is commonly associated with severe lung disease and inflammatory damage (Li 2016).

The proposed sample size combines a power calculation and a consideration of logistical constraints. We expect to see 290 patients per year of which 50% should complete a SNOT-22 form. Of the 145 forms received around 72 (50%) should be above average. If we allow for a low recruitment rate (of 30-40%) we believe it is realistic to enrol at least 20-30 patients per year. Over the 18 months of the project we feel, therefore, a sample size of 30-40 can be realistically achieved. Savastano (2014) published summary details of SNOT-22 scores for CF patients (who should well approximate our sample group) reporting a mean (SD) scores of 30.5 (14.5). We draw our definition of a clinically significant change from Hopkins et al (2009), who propose 8.9 points. The study will be structured as a 2-sided equality trial, with before and after measurements for each participant. In order to obtain a power of 80% we would require a sample size of at least 21.

We appreciate that the numbers of participants that will be recruited for this study, within the time frame (between 20-40 in 18 months), is not a true representation of the national population of CF patients. However, the results of this feasibility/pilot study will identify any trends in the effects of a nasal rinse supplemented with manuka honey on the bacterial amount/diversity within the infected sinuses. Antimicrobial interventions that do not rely on antibiotics to remove resistant strains from sinus infections have the potential to help alleviate symptoms in the sinus and upper airways, which may impact on the bacteria seen in the lower airways (Aanaes, 2013). Therefore, if a change in Project Proposal – V6.0 - 07/09/2020

bacterial diversity or a reduction in symptoms is observed, this study could inform a more in-depth study as manuka honey has already been demonstrated to eradicate both antibiotic sensitive and AMR bacteria in vitro and from chronic in vivo wounds.

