9.4 Randomisation, Blinding, and Unblinding

A blocked randomisation list will be generated prior to start of study using the electronic random number generator tool (see below). The participants of the study will not be blinded to the treatment they are receiving because the addition of manuka honey to the sinus rinse is obvious and there is no way to negate this. The academic research team will be blinded to which groups the participants (only identifiable by their participant ID number) are assigned. This information (the group allocations and treatment regimens) will only be made available to the academic research team once analysis of the data begins.

- GraphPad QuickCalcs
 - o https://www.graphpad.com/quickcalcs/randomize1/

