9.8 Discontinuation/Withdrawal of Participants

All participants have the right to withdraw from the study at any time. In addition to this, the chief investigator (CI) may discontinue a participant from the study at any time if the they consider it necessary. The reason for withdrawal will be recorded on the CRF. The participant will be replaced if possible within the time frame using the same recruitment procedure as was used for the original participant. If you wish to withdraw from the study, all identifiable samples will be destroyed, however all the data generated up to the date of your withdrawal will remain for analytical purposes. Withdrawing from the study will in no way affect your current or future care. If in the future, you were no longer able to give consent to partake in the study, we would follow the procedure as if you had withdrawn from the study

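### The sample size of 21 for 80% power is a single-group before/after figure; for the two-arm primary comparison, 30 participants give about 37% power, or 46–77% with baseline adjustment at assumed correlations of 0.5–0.8

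*Combined protocol and SAP*

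**What the plan says.** Section 12.2 takes an SD of 14.5 from published SNOT-22 scores in cystic fibrosis and a clinically significant change of 8.9 points. It describes a two-sided equality design with before and after measurements on each participant, and concludes: "In order to obtain a power of 80% we would require a sample size of at least 21". It then sets a target of 30, "since this will be both achievable and will deliver sufficient power, even allowing for drop outs". Section 3 repeats the 21.

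Section 12.3 defines the primary outcome as a comparison between arms: the "primary outcome measures will be to determine whether the SNOT-22 score of the manuka honey treatment group has improved compared to the standard treatment". Section 12.1 has the "scores being assessed before and after treatment within and between both patient groups", but names no test and no baseline adjustment for SNOT-22.

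On allocation, section 9.4 says only that "A blocked randomisation list will be generated prior to start of study"; no ratio is given. On dropout, section 12.3 says "If any participants withdrew before the second visit/second set of samples were taken then that data will be excluded from analysis", and section 9.8 says "The participant will be replaced if possible within the time frame". Alpha, a dropout rate and a before/after correlation are not stated anywhere.

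**The concern.** The sample-size calculation has one group in it and the primary comparison has two. A difference between two independent means has twice the variance of a single mean from a group of the same size. Each arm therefore needs about twice the single-group number, and the trial about four times. The plan instead treats the single-group number as the total across both arms, because 30 in total is said to exceed it with room for dropouts.

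What is at stake is how the result will be read. Section 3 says that if a change in "bacterial diversity or a reduction in symptoms is observed, this study could inform a more in-depth study". A reader who relies on section 12.2 would take a non-significant between-arm result as adequately powered evidence against honey, and would not expect a confidence interval that may be wider than the 8.9-point effect in either direction.

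**Working it through.** **Inputs from section 12.2:** difference 8.9; SD 14.5; two-sided test; power 80%; target 30 in total.

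**Assumptions:** alpha 0.05; 1:1 allocation; where stated, a before/after correlation r of 0.5, 0.7 or 0.8.

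**1. Reproduce the 21.** Single-group normal formula:

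n = (1.960 + 0.842)² × 14.5² / 8.9² = 20.83, rounded up to 21.

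Two-sided alpha of 0.10 would give 16.4 and 0.01 would give 31.0, so of the usual levels only 0.05 fits. (A paired t-test calculation gives 76% power at 21 and needs 23.)

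**2. Same inputs, two arms.** n per arm = 2 × 20.83 = 41.67, rounded up to 42. By the two-sample t-test, power is 79.4% at 42 per arm and 80.3% at 43. The total is 84–86.

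**3. Power at 15 + 15, SD 14.5.** Standard error = 14.5 × √(2/15) = 5.29; noncentrality = 8.9 / 5.29 = 1.68; df 28. Power is 36.8%. This applies if 14.5 is the SD of whatever quantity is compared, including the SD of change.

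**4. If 14.5 is the SD of single scores.** Change-score SD = 14.5 × √(2(1 − r)). Baseline-adjusted SD = 14.5 × √(1 − r²), with one df lost (df 27).

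| r (assumed) | Change SD | Power, change score, N = 30 | Adjusted SD | Power, adjusted, N = 30 | Total N for 80%, adjusted |
|---|---|---|---|---|---|
| 0.5 | 14.50 | 37% | 12.56 | 46% | 66 |
| 0.7 | 11.23 | 55% | 10.36 | 62% | 46 |
| 0.8 | 9.17 | 73% | 8.70 | 77% | 34 |

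For 80% at N = 30 with nobody lost, r must be about 0.82 with adjustment, or 0.83 for change scores. A 4,000-run simulation at r = 0.7 agreed: 61% adjusted, 56% for change scores.

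**5. Dropout.** No rate is given, so take as a scenario that 21 are analysed, the number the plan calls enough. At 10 + 11, power is 27% with SD 14.5, and 34%, 46% or 60% with adjustment at r = 0.5, 0.7 or 0.8. Reaching 80% would need r of about 0.88.

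**6. Precision at 15 per arm.** The 95% CI half-width is t × SD × √(2/15). Unadjusted: 2.048 × 5.29 = 10.8 points. Adjusted: 9.4, 7.8 and 6.5 points at r = 0.5, 0.7 and 0.8.

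**7. Readings that might rescue the claim.**
- *21 per arm:* excluded, because a target of 30 in total is said to cover it.
- *Within-group change in the honey arm:* the 21 would then be needed in that arm alone; about 15 there gives 60% power (one-sample t-test).
- *Both arms pooled, before versus after:* this reaches 21 but cannot show what adding honey does.
- *Unequal allocation:* worse; 20:10 gives 33%.
- *Recruiting the upper limit of 40:* 47% with SD 14.5.

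**The case against.** The best defence is that this is labelled a feasibility or pilot study. Section 3 concedes that the numbers are not representative and speaks of identifying trends, and section 12.2 already names logistics as one basis for the size. A pilot need not be powered. That is true, and it is why no increase in size is asked for. It does not excuse the sentence at issue, because the plan itself claims sufficient power.

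A second objection is about method: the plan's 21 rests on the normal approximation, while the powers above use the t distribution. On the normal basis, power at N = 30 is 39% with SD 14.5, and 49%, 65% and 80% with adjustment at r = 0.5, 0.7 and 0.8. So at r = 0.8 with 30 completers the adjusted analysis is borderline. This stands as a qualification at the top of the range and does not alter the rest.

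Third, the correlations are not from the documents. They are assumptions, shown because adjustment is the plan's most favourable route. With 40 participants and adjustment, power would be 59%, 75% and 88% at the same three values. The plan, however, specifies neither the adjustment nor a correlation, and its stated target is 30.

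Fourth, section 8 says the recruitment estimate already considers dropout, and section 9.8 allows replacement where possible. That softens the dropout scenario, but the shortfall exists with no dropout at all.

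**Conclusion.** The concern holds, and the text must be corrected. The arithmetic behind 21 is sound for a single group and does not apply to the primary comparison, which needs 84–86 participants on the same inputs. With 30 analysed, power is about 37% if the SD of the compared quantity is 14.5. If 14.5 is the SD of single scores, it is about 46–77% with baseline adjustment over assumed correlations of 0.5 to 0.8. The assurance about dropouts falls with the power claim.

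These figures rest on two-sided alpha 0.05, supported by the exact reproduction of 21, and on 1:1 allocation, which favours the plan. The adjusted figures also rest on correlations that the documents do not supply.

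**What to change.** In section 12.2, replace the last two sentences with text such as:

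> A single-group before/after comparison needs about 21 participants for 80% power (change 8.9, SD 14.5, two-sided alpha 0.05, normal approximation). The primary comparison is between two arms. With 30 analysed (15 per arm), power by t-test for an 8.9-point between-arm difference is about 37% if the SD of the compared quantity is 14.5. If 14.5 is the SD of single scores and the before/after correlation is 0.5–0.8 (assumed), power is about 46–77% with baseline adjustment. The target of 30 is chosen on feasibility and precision: the expected 95% CI half-width is 10.8 points unadjusted, and 9.4, 7.8 or 6.5 points at correlations of 0.5, 0.7 or 0.8. A non-significant result is not evidence of no effect.

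Amend the opening sentence of section 12.2, and its repeat in section 3, so that neither still presents the size as resting on a power calculation. In section 3, label the 21 as the single-group figure. In section 12.3, name the between-arm difference with its 95% CI as the primary result, and state alpha, the allocation ratio and whether baseline SNOT-22 is adjusted for.

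The cost is wording in three sections. Recruitment and conduct do not change and no extra patients are needed; the stated power becomes less favourable.
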